#### Accuracy

For people with Mild AD dementia or MCI due to AD reference ranges are available from research cohorts and P-tau 181 alone has an Area Under Receiver Operating Characteristic curve (AUROC) of 0.80 compared to amyloid PET [23] and the combination of NFL and P-tau 181 has an AUROC of 0.88 compared to delayed verification of AD (sensitivity 83-88%, specificity 82-83%) to identify people who have progressive AD pathology as a cause of their MCI at baseline. Simple cognitive tests carried out in clinic such as the Montreal Cognitive Assessment have 90% and 100% sensitivity for MCI and mild AD dementia respectively, with specificity varying according to the cohort (up to 87% when comparing to healthy control in a research cohort) [24]. For people without AD – cerebrospinal fluid (CSF) biomarkers have a very high negative predictive value (94% on a real-world sample after median 4.7 years follow-up). Modelling suggests that combining blood biomarkers with simple cognitive tests will be more sensitive and specific than either test alone.

SleepAD Protocol v6.0 6th September 2024

As blood biomarkers make large scale interventional studies possible in AD at vastly reduced expense (as we can avoid CSF testing or PET scanning), new therapeutic targets for intervention can be tested more rapidly.

The value of blood biomarkers is ultimately determined by the accuracy with which they can predict future AD, and therefore collecting longitudinal data is essential, with progression from MCI to AD as the key outcome of interest. To this end, our pre-clinical/MCI cohort will be followed up at 2 and 5 years after their involvement in the study, to check whether their diagnosis has converted to AD or another dementia. Diagnostic accuracies of all included biomarkers will be assessed, and we will use modelling to examine how specific biomarkers improve dementia risk prediction when combined with baseline demographic and clinical information.

Molecular classification of AD is important alongside exploration of sleep as several studies have suggested distinct interaction between different underlying AD pathology (amyloid, tau or other) and different sleep metrics e.g. [17, 25]. Only by deep characterisation of sleep phenotype as in SleepAD, can we develop clinical trials that target the right sleep treatment to the right patient.

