### 2.1.3 Secondary Objectives

#### Theme 1

SleepAD Protocol v6.0 6th September 2024

- 2.1.3.1 Sensitivity of home high-density EEG to detect behaviourally relevant sleep neurophysiology
- 2.1.3.2 Feasibility of using concurrent overnight pulse oximetry to screen for obstructive sleep apnoea (OSA)

### Theme 2

- 2.1.3.3 Accuracy of blood biomarkers for AD compared to CSF testing;
- 2.1.3.4 Explore the relationship between blood biomarkers, *APOE* carrier status and sleep metrics in subgroup who have had both.
- 2.1.3.5 Diagnostic sensitivity of blood biomarkers for predicting progression to AD.
- 2.1.3.6 Characterisation of the relationship between CSF orexin and blood biomarkers in predicting sleep-wake disturbance and disease status

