#### 4.2 Inclusion Criteria

### For Sub-Study 1

- 1. Age > 50
- 2. All participants must express that they are willing to take part in this study and adhere to the study procedures
- 3. Full capacity to consent to involvement
- 4. Clinical diagnosis of MCI due to AD[52] or mild AD[51] according to standardised criteria

(NB people with a mixed AD/Vascular dementia diagnosis are eligible for inclusion)

### For Sub-Study 2

- 1. All participants undergoing CSF testing clinically including CSF biomarkers of AD.
- 2. All participants must express that they are willing to take part in this study and adhere to the study procedures.
- 3. Full capacity to consent to involvement

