#### Follow-up checks of medical records

Medical records from participants in both substudies will be checked again at 2 years and at 5 years after involvement in the study. This will only include available records from those participants in the pre-clinical/MCI phase at time of participation in the study. In both substudies, the date will be measured from the date of the last participant's venepuncture. This follow-up data will be extracted to identify whether the pre-clinical / MCI diagnosis has changed to a dementia diagnosis.

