#### Data analysis will:

- a) Quantify the proportion of lost/degraded blood samples, and data completeness for memory tests
- b) Calculate diagnostic accuracy of the separate index tests (NFL, p-tau) for AD, at prepublished thresholds, compared to reference standard (CSF), via AUROC curves[65]
  - and explore heterogeneity in diagnostic accuracy of index tests AD by prespecified factors listed using cut offs for AD | no AD extrapolated from UCL clinical laboratories.
- Quantify the relationship between p-tau, NFL and sleep metrics in patients who have had both blood biomarkers and high-density EEG
- d) As a post hoc analysis, we will explore the diagnostic accuracy of Montreal Cognitive Assessment (MoCA) as a standard clinical test and visually compare accuracy of NFL and tau to that of MoCA.
- e) Where CSF is available, we will run biomarker analyses on the UCL research SIMOA machine to internally validate samples also tested as part of routine clinical care on the UCL clinical laboratory SIMOA machine.
- f) Once longitudinal data has been collected from our pre-clinical/MCI cohort, we will calculate the diagnostic accuracy of the separate index tests for AD via AUROC curves. The relationship between conversion to AD and the index tests will be assessed using regression models with age, sex, baseline MoCA score, plasma: CSF orexin ratio, and baseline APOE carrier status as covariables.

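### Conversion is extracted as any dementia but analysed as conversion to AD, with no rule for other dementias; in sub-study 2 the AD label may partly reflect baseline CSF, which can inflate p-tau's apparent prognostic accuracy.

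*Protocol*

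**What the plan says.** The protocol describes the follow-up event in different ways.

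- Section 8.2 (follow-up checks of medical records), which governs data collection: "This follow-up data will be extracted to identify whether the pre-clinical / MCI diagnosis has changed to a dementia diagnosis". Type of dementia and date of diagnosis are not mentioned.
- Section 1.1, Accuracy: the pre-clinical/MCI cohort is followed "to check whether their diagnosis has converted to AD or another dementia". The same paragraph describes the collection of longitudinal data "with progression from MCI to AD as the key outcome of interest".
- Objective 2.1.3.5: "Diagnostic sensitivity of blood biomarkers for predicting progression to AD".
- Section 10.2, substudy 2, item f): AUROC curves for AD, and then "The relationship between conversion to AD and the index tests will be assessed using regression models". The listed covariables are age, sex, MoCA at baseline, the ratio of plasma to CSF orexin, and APOE status. Baseline CSF status for AD is not among these covariables.

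Entry to sub-study 2 is defined by clinical CSF testing: "All participants undergoing CSF testing clinically including CSF biomarkers of AD" (section 4.2). Section 4.1 adds that CSF is tested in early disease or where the diagnosis is unclear. Item b) of section 10.2 uses CSF as the reference standard for the same plasma tests. Follow-up diagnoses come from medical records at 2 and 5 years. No adjudication, no blinding to CSF and no rule for assigning AD or another dementia is described.

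**The concern.** There are two linked problems. First, the extraction in section 8.2, taken as written, does not supply the outcome analysed in item f). Where someone develops another dementia, nothing says whether that person is a control, is excluded or forms a separate category. Such people are to be expected: sub-study 2 has no exclusion for non-AD dementia, and section 1.1 anticipates them.

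Second, the CSF test is done to help reach a diagnosis, and its result normally sits in the record before any conversion. If the clinician who later names the dementia relies on it, the AD label partly carries the baseline CSF result. A plasma marker that agrees with CSF then separates AD converters from the rest even if it says nothing about who will decline. Item f) has neither an all-cause outcome nor an adjustment for CSF status, so it cannot tell the two explanations apart. Section 1.1 says that the value of blood biomarkers ultimately rests on predicting future AD, so the distinction matters for how the result is read.

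**Working it through.** **The plan's own figure.** Section 10.1 gives a marginal error of 0.08 for AUROC 0.9, 50% prevalence and N = 100. Treating 0.9 as a proportion in 50 people gives 1.96 × √(0.9 × 0.1 / 50) = 0.083, which rounds to it. Hanley-McNeil gives 0.063 and the Obuchowski binormal formula 0.073; the plan does not name its formula. The figure concerns the cross-sectional classification. None is given for item f), so it does not bear on this point.

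**Inputs for the illustration**

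- Share CSF-positive: 50%. This is the section 10.1 prevalence, assumed to hold in the pre-clinical/MCI subset.
- Plasma-CSF AUROC, A: 0.90 (section 10.1) down to 0.80 (section 1.1, P-tau 181, but against amyloid PET rather than CSF).
- Conversion to any dementia, c: 30 to 50%. This is an assumption; the protocol gives no rate.
- Conversion unrelated to CSF or plasma, so the all-cause prognostic AUROC is 0.50.
- A share a of CSF-positive and b of CSF-negative converters labelled AD. Both are assumptions.
- Everyone not labelled AD serves as a control. This is an assumption, because item f) is silent.

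**Formula.** Let g be the CSF-positive share among AD converters and f the share among controls. Then

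AUROC = 0.5 + (A − 0.5)(g − f), with g = a/(a + b) and f = (1 − ac)/(2 − (a + b)c).

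**CSF fully sets the label (a = 1, b = 0).** Here g = 1 and f = (1 − c)/(2 − c).

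- c = 0.3: f = 0.7/1.7 = 0.412. A = 0.80 gives 0.5 + 0.3 × 0.588 = 0.676; A = 0.90 gives 0.5 + 0.4 × 0.588 = 0.735.
- c = 0.5: f = 0.5/1.5 = 0.333. A = 0.80 gives 0.700; A = 0.90 gives 0.767.

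**Partial reliance, 70%/30%.** Here g = 0.7.

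- c = 0.3: f = 0.79/1.7 = 0.465. A = 0.90 gives 0.5 + 0.4 × 0.235 = 0.594.
- c = 0.5: f = 0.65/1.5 = 0.433. A = 0.90 gives 0.5 + 0.4 × 0.267 = 0.607.

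| Converters labelled AD (CSF-positive / CSF-negative) | A = 0.80 | A = 0.90 |
|---|---|---|
| 100% / 0% | 0.68 to 0.70 | 0.74 to 0.77 |
| 90% / 10% | 0.64 to 0.66 | 0.69 to 0.71 |
| 70% / 30% | 0.57 to 0.58 | 0.59 to 0.61 |
| 50% / 50% (label unrelated to CSF) | 0.50 | 0.50 |

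Ranges run over c = 0.3 to 0.5. A simulation with 400,000 people per scenario agrees to within 0.002. In it, all-cause dementia as the outcome, or analysis within CSF-positive people, returns 0.50.

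**If other-dementia converters are dropped instead of used as controls.** With the label fully set by CSF, f = 0.5, so the AUROC is 0.5 + 0.4 × 0.5 = 0.70 at A = 0.90 and 0.65 at A = 0.80. Dropping them reduces the inflation but does not remove it.

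**The case against.** Much can be said for the plan.

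- Section 1.1 speaks of AD or another dementia, so type may well be intended for capture, and form fields and outcome coding are often left to a SAP. This softens the mismatch. It does not remove it, because section 8.2 is the operative text and does not ask for type or date.
- A reader might infer that people who develop another dementia are counted as non-converters. The protocol does not say so; it gives no handling at all.
- A reader might also take it as fact that the follow-up label is made with CSF in hand. No section describes how the diagnosis is reached. The inference is reasonable for sub-study 2 given sections 4.1 and 4.2. In sub-study 1 it applies only where routine CSF results exist (section 6.1). Plasma results are not fed back (section 11.5), so any effect runs indirectly, through CSF.
- The mechanism fits p-tau. Section 1.1 describes NFL as a marker of neurodegeneration from any cause, so close agreement with CSF status for AD should not be assumed for it.
- Progression to AD is a legitimate target, and telling future AD from other outcomes is part of it. The 0.50 benchmark belongs to all-cause dementia, which is a different question.
- Conversion wholly unrelated to CSF is an extreme assumption. Section 1.1 cites a 94% negative predictive value for CSF over a median of 4.7 years. If few CSF-negative people convert, CSF has few labels to decide and the inflation shrinks.

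These points limit the size and reach of the problem. They do not give item f) a way to separate prognosis from agreement with CSF.

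**Conclusion.** The point holds as a mismatch of outcomes together with a plausible, unquantified route to inflation, mainly for p-tau in sub-study 2. The 0.68 to 0.77 range is an upper bound: it needs CSF to decide every label and conversion to be unrelated to CSF. At plasma-CSF AUROC 0.9 with 70%/30% labelling the figure is about 0.60, and with a label unrelated to CSF it is 0.50. The conversion rates and labelling shares are assumptions.

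A reader might go further and conclude that item f) largely re-measures cross-sectional agreement, or that the objective could be declared met by a marker with no prognostic value. The documents do not support that. The first holds only near the extreme case, and the protocol sets no success threshold for item f). This is a secondary analysis in a feasibility study, but the remedy is nearly free and the follow-up checks fall 2 and 5 years after the last participant.

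**What to change.** In section 8.2, have the 2-year and 5-year checks record the type of dementia and the date of diagnosis.

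In section 10.2, substudy 2, item f):

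- report all-cause dementia alongside AD dementia;
- treat other dementia as a separate, competing outcome rather than as non-conversion;
- add a sensitivity model adjusted for baseline CSF status for AD, where available.

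An AUROC within CSF-positive participants should be exploratory only. Even if all 100 sub-study 2 participants were pre-clinical or MCI, 50% prevalence would leave 50 people, with 15 to 25 converters at 30 to 50% conversion. The real subset will be smaller.

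The cost is two extraction fields and one more set of models, with no new participant contact. The estimates may look less favourable.

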#### 11 SUMMARY OF SAFETY AND ETHICAL CONSIDERATIONS

### 11.1 Risks associated with self-report questionnaires and cognitive testing

There are no serious risks involved in completing the experimental tasks and questionnaires. Similar cognitive testing is undertaken regularly by researchers in this group, and almost all patients tolerate it and many enjoy it. Occasionally patients are bored or frustrated by testing and, in that case, we offer them the opportunity to have a break and continue later. The participants also know they are allowed to withdraw their participation at any time.

### 11.2 Sleep recording

The sleep recordings carry no risks above those encountered in life outside research participation. There is the possibility of a localised skin reaction as a result of wearing the electrodes. If participants report pre-existing irritable skin, the researcher will remain with the patient for up to 2 hours while wearing the device for the first time to ensure irritation is not an issue. EEG recordings are safe and are a non-invasive procedure. To our knowledge, no complications other than skin irritability have been reported previously.

### 11.3 GP involvement

We will send each participant's GP a letter explaining that the volunteer is taking part in this study. The GP will not be routinely contacted about our findings. However, if the researchers discover a suspected illness (such as undiagnosed Parkinson's disease, sleep apnoea), the Principal Investigator will be informed and subsequent steps may include a direct referral for appropriate specialist follow-up or communication with the participants' GP to facilitate this. This procedure will be explained to the participants in the PIS and participants can agree to GP involvement in case of incidental findings by signing the consent form. In the event results

SleepAD Protocol v6.0 6th September 2024

suggest an unexpected significant clinical finding, participants who do not agree to this on the consent form will be contacted to discuss this further.

#### 11.4 Discontinuation Criteria

#### 11.4.1 For individual participant/consultation

The participant will be withdrawn from the study if the clinician asked to evaluate the screening information does not think it is safe for them to participate.

In addition, if for any reason at all a participant wishes to withdraw their participation from the study, they may do so at any point.

If the participant is happy for us to do so, and if the reason for withdrawal is not one that is likely to affect the data gathered, we will keep data already collected for analyses. If not, all information relating to that participant will be safely disposed of, providing the data has not been analysed. If there has been an adverse effect, this will be recorded accordingly.

If a participant withdraws or is withdrawn from the study, another participant will be recruited to replace them.

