#### 2.1.2 Primary Objectives

### Theme 1

2.1.2.1 Feasibility of home high-density EEG (primary objective);

2.1.2.2 Acceptability of home EEG;

#### Theme 2

2.1.2.3 Feasibility of blood biomarkers for AD;

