### 5.5 Withdrawal of Participation

Participants are free to withdraw from the study and to opt-out at any point or a participant can be withdrawn by the Investigator. If withdrawal occurs, the participant will have the option as to whether they wish to allow previously collected data to be utilised for ongoing research. The reason for withdrawal will be documented in the participant's case report form (CRF) although a reason would not have to be provided.

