### 6.3 Main Study Assessments

#### For Substudy 1

- Venepuncture of 5-10 ml blood biomarkers taken for analysis of biomarkers (P-tau & NFL, GFAP and abeta42/40, and possibly others in future). The blood sample will either be arranged to be taken during a routine clinical appointment venepuncture at the Brain Centre (i.e. not an extra venepuncture), or during a separate appointment (which would require a new venepuncture).
- Sleep recording participants will undergo EEG recording at home for 3 nights and will also complete a Consensus Sleep Diary questionnaire [62] each night. The sleep monitoring will be performed using high-density at-home EEG equipment which will be set up by the researcher in the participant's home. This will involve participants undergoing full polysomnography (PSG), where electrophysiological data from electrodes placed on the scalp, face and body will be recorded. The home setup is designed to closely replicate the setup used in sleep laboratories. Participants will wear a 32-channel sleep cap including scalp and auxiliary channel location using a wireless LiveAmp 32-channel active electrode system (Brain Products UK). EEG recordings are acquired on an internal memory system and will subsequently be downloaded to a secure University of Bristol server. Although we do not currently have experience of sleep recordings in Alzheimer's disease, we have experience from recording sleep in patient populations of similar age, living with chronic pain. In our experience, these patients tolerate sleep recordings

SleepAD Protocol v6.0 6th September 2024

- well. Numerous EEG studies in Alzheimer's disease are reported in the literature, as reviewed elsewhere [63].
- Pulse oximetry participants will be asked to undergo two nights of overnight pulse oximetry (concurrent with EEG recording) during the 3 night window of sleep recordings. A pulse oximeter is a device routinely used in NHS practice to collect pulse oximetry data, and will be used in line with NHS protocols to monitor pulse and oxygen saturation levels and screen for obstructive sleep apnoea (OSA). Overnight pulse oximetry is an accepted and widely used screening tool for moderate to severe OSA [64]. Those with abnormal results will be offered referral to the Non-invasive Ventilation Clinic and their GP will be informed with the participant's consent.

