#### 9.5 Data Loss

The technology used in the study will be set up for each participant according to a rigorous protocol agreed by the research team, and participants are provided with written and verbal information on study activities to ensure adherence to protocol. However due to the remote and technology-focused nature of the study, it is possible for data to be lost or not collected due to technological issues (e.g., battery failures).

If a significant portion of data is missing on a given task, participants may be asked if they are willing to repeat an EEG night or blood test if appropriate within the 3 month study period. The participant can decline repeating any measures without this affecting their participation in the study. Similarly, if appropriate in the opinion of the Chief Investigator, participants may be asked to complete study activities outside of their main study period if study protocol has changed (and participants will be reconsented as appropriate).

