### 10.2 Proposed Analyses

#### For Substudy 1

Data analysis will:

- a) Quantify the proportion of missing data for sleep nights with high density EEG. Post hoc analysis will also explore whether any baseline questionnaire outcomes associate with poor data quality (larger levels of missing data)
- b) Calculate acceptability ratings for home EEG
- c) We will analyse non-REM duration from high density EEG and assess whether or not we can replicate the observed association between sleep metrics and memory observed from laboratory polysomnography, e.g. in the DOPAMIND study, when using home high density EEG.
- d) Quantify the proportion of datasets for sleep nights with pulse oximetry which are sufficiently complete to enable clinical screening for Obstructive Sleep Apnoea.

### For Substudy 2

Analysis of samples: will be on using the SIMOA platform for research use.

SleepAD Protocol v6.0 6th September 2024

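### The reason-based disposal of withdrawn participants' data in 11.4.1 can erase EEG failures from the primary feasibility outcome, and it contradicts 5.5 and 14.2.1

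*Protocol*

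**What the plan says.** Section 2.1.2 names feasibility of home high-density EEG as the primary objective. Section 6.3 sets the schedule: "participants will undergo EEG recording at home for 3 nights". The matching analysis, 10.2(a) for sub-study 1, is to "Quantify the proportion of missing data for sleep nights with high density EEG". It is followed by a post hoc look at whether baseline questionnaires are associated with poor data quality. No denominator is given.

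Section 11.4.1 governs withdrawal. Subject to the participant's agreement, "if the reason for withdrawal is not one that is likely to affect the data gathered, we will keep data already collected for analyses". It continues: "If not, all information relating to that participant will be safely disposed of, providing the data has not been analysed". It ends: "If a participant withdraws or is withdrawn from the study, another participant will be recruited to replace them".

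Two other sections deal with the same records:

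- Section 5.5 says that "the participant will have the option as to whether they wish to allow previously collected data to be utilised for ongoing research". It applies no test based on the reason, and it has the reason recorded in the CRF, although the participant need not give one.
- Section 14.2.1 requires completed and signed CRFs for every enrolled participant, explicitly including non-completers, and a Withdrawal Form noting the reason for withdrawal during the experimental phase.

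On failed recordings, 9.5 says that where much of the data is missing, "participants may be asked if they are willing to repeat an EEG night or blood test if appropriate within the 3 month study period".

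**The concern.** In most studies a withdrawal is a nuisance. Here it is part of the primary outcome. A participant who stops after one night because the cap was intolerable has shown that home EEG was not feasible for that person. Such a reason can readily be judged to bear on the data, and that judgement triggers disposal under 11.4.1. The participant's place is then filled by someone else.

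Three things are at stake:

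- **The primary proportion.** If withdrawn people vanish from the records, the missing-data figure describes only those who tolerated the procedure, and it moves towards a finding of feasible.
- **The analysis of who has poor data.** Disposal covers all of the participant's information, so it takes the baseline questionnaires that 6.2 and 10.2(a) rely on to identify in whom home EEG works.
- **Acceptability.** This also sits under the primary objectives in 2.1.2, and any response from the same people would be lost.

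A missing denominator could be supplied in a statistical analysis plan. Deleted records could not be.

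**Working it through.** **1. The retention rules side by side**

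| Section | Who or what decides | Consequence |
|---|---|---|
| 5.5 | The participant alone | Data kept if the participant allows it; any reason documented |
| 11.4.1 | Participant's agreement and a test of the reason | If either fails, all information discarded unless already analysed |
| 14.2.1 | Not optional | CRFs and Withdrawal Form for non-completers |

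Take a participant who agrees to retention but left because of the EEG. Under 5.5 the data may be used. Under 11.4.1 they can be discarded. Under 14.2.1 the CRF and Withdrawal Form must exist. These cannot all be followed.

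**2. Can the bias be computed from the protocol?** No. It states no expected withdrawal rate, night-failure rate or repeat rate. The sub-study 1 sample size (50 in 4.4, 50–100 in 10.1) is justified only by suitable precision, with no inputs, so there is no stated figure to reproduce.

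**3. Illustration under assumed rates.** Let w be the share of EEG starters who withdraw after night 1, and m the failure rate of any attempted night. Each participant has 3 scheduled nights.

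- Missing proportion over all starters: w(2/3 + m/3) + (1 − w)m.
- Missing proportion if every withdrawn participant is deleted and replaced: m.
- Difference: w(2/3 + m/3) + (1 − w)m − m = (2/3)·w·(1 − m).

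| w | m | All starters | Withdrawn removed | Gap (points) |
|---|---|---|---|---|
| 5% | 10% | 13.0% | 10% | 3.0 |
| 5% | 20% | 22.7% | 20% | 2.7 |
| 10% | 10% | 16.0% | 10% | 6.0 |
| 10% | 20% | 25.3% | 20% | 5.3 |
| 20% | 10% | 22.0% | 10% | 12.0 |
| 20% | 20% | 30.7% | 20% | 10.7 |

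Example, w = m = 20%: 0.2 × (0.6667 + 0.0667) + 0.8 × 0.2 = 0.1467 + 0.16 = 0.307.

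These gaps assume that every withdrawal is deleted. If only a share d is deleted and the rest are counted with their lost nights, the gap is (2/3)(1 − m)[w − w(1 − d)/(1 − wd)]. With w = m = 20% and d = 50% this is 0.5333 × (0.2 − 0.1/0.9) = 0.047, or 4.7 points instead of 10.7.

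**4. The same check in whole participants.** Suppose 50 are retained with 10% of their 150 nights missing (15 nights), and 10 others withdrew and were replaced.

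- No usable nights before leaving: (15 + 30)/180 = 25.0% over all 60, against 10.0% among the 50.
- One usable night each: (15 + 20)/180 = 19.4%.
- With 3 to 5 withdrawals instead of 10, the gap is about 3 to 8 points.

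**5. Scale.** The 95% half-width for a participant-level proportion of 0.9 with n = 50 is 1.96 × √(0.9 × 0.1/50) = 0.083. The gaps at 5–10% withdrawal lie inside 8.3 points, and those at 20% lie outside it.

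**The case against.** The strongest reply is that the text does not show a biased result. Several stronger readings are tempting and go further than the protocol does:

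- **That replacement itself biases the outcome.** Section 11.4.1 says that a replacement is recruited. It does not say that the withdrawn person leaves the proportion. If withdrawals stay in the denominator, replacement does no harm. It also covers people withdrawn at screening for a low MoCA (5.3) or on safety grounds (11.4.1), before any EEG, who are not a source of this bias.
- **That repeated nights overwrite failures.** Section 9.5 makes repeats optional and never says that a repeat takes the place of the first attempt. Section 9.2.2 keeps raw sleep recordings for 20 years, so first attempts by retained participants stay countable.
- **That the blood-sample outcome suffers in the same way.** Lost or degraded samples are a sub-study 2 outcome, and 8.2 says that venepuncture there happens only once. That wording and the repeat blood test in 9.5 need reconciling, but no bias follows from them.
- **That a later trial would be under-sized.** The protocol states no progression threshold and no rule for sizing a later trial from this figure.

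All four points stand. It is also fair that a reason affecting the data could mean an illness that invalidated a recording, not intolerance of the cap, and that disposal does not apply once data have been analysed.

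These points do not rescue the disposal rule. On either reading of the reason, the participant started EEG and did not complete it, and 10.2(a) should count that. Disposal is a conduct rule written in the protocol, it conflicts with two other sections, and its effect cannot be reversed.

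**Conclusion.** The concern holds for the disposal rule combined with replacement and no stated denominator. Together these can remove EEG-related withdrawals from the primary feasibility measure, and any such effect runs towards feasible. The contradiction with 5.5 and 14.2.1 is plain from the text and needs no assumption.

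The bias is a risk, not a demonstrated amount. If 5–20% of starters withdraw after the first night, 10–20% of attempted nights fail, and every withdrawn participant is dropped, missingness is understated by about 3 to 12 points. It is less if only some are dropped. All of these rates are assumptions. The repeat-night and blood-test provisions are matters to clarify, not further proven biases.

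**What to change.** - **11.4.1:** delete the condition based on the reason for withdrawal and follow 5.5, so that the participant decides. Where a participant asks for data to be removed, respect that, but keep a non-identifying count of the withdrawal, with the reason where one was given. Align this with the CRF and Withdrawal Form requirements in 14.2.1.
- **10.2(a):** define the feasibility denominator as all consented participants who passed screening and were due to start EEG, times 3 scheduled first-attempt nights. Count nights lost to withdrawal as missing. Report nights recovered by repeat (9.5) separately.
- **Replacement:** may stay, provided replacements are added to the denominator and not substituted for those who withdrew. Screening withdrawals before EEG are unaffected.
- **9.5 and 8.2:** reconcile the repeat blood test with the single venepuncture stated for sub-study 2.

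The cost is protocol wording only, with no extra participants or measurements. The reported feasibility figure may be less favourable. The change should be made before the disposal rule is applied to any further withdrawal.
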